6.2.2. Safety Endpoints

All safety analyses will be performed on the Safety Analysis Set.

Safety data will be presented in tabular and/or graphical format and summarized descriptively, where appropriate.

6.2.2.1. Adverse Events

TEAEs will be reported in accordance with the CaPS.

Participant discontinuations due to adverse events will be detailed by treatment. Data will be reported in accordance with the CaPS.

6.2.2.2. Laboratory Data

Laboratory data will be listed and summarized by treatment in accordance with the CaPS.

6.2.2.3. Vital Signs

Vital sign data will be databased and available upon request.

6.2.2.4. Electrocardiograms

ECG data will be databased and available upon request.

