9. STATISTICAL CONSIDERATIONS

Detailed methodology for summary and statistical analyses of the data collected in this study is outlined here and further detailed in the SAP, which will be maintained by the sponsor. The SAP may modify what is outlined in the protocol where appropriate; however, any major modifications of the primary endpoint definitions or their analyses will also be reflected in a protocol amendment.

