9.3.3. Secondary Endpoint(s) Analysis

9.3.3.1. Safety Analyses

All safety analyses will be performed on the safety population.

AEs, ECGs, BP, pulse rate, and safety laboratory data will be reviewed and summarized on an ongoing basis during the study to evaluate the safety of participants. Any clinical laboratory, ECG, BP, and pulse rate abnormalities of potential clinical concern will be described. Safety data will be presented in tabular and/or graphical format and summarized descriptively, where appropriate.

Medical history, physical examination, and neurological examination information, as applicable, collected during the course of the study, will be considered source data and will not be required to be reported, unless otherwise noted. However, any untoward findings identified on physical and/or neurological examinations conducted during the active collection period will be captured as AEs, if those findings meet the definition of an AE. Data collected at screening that are used for inclusion/exclusion criteria, such as laboratory data, ECGs, and vital signs, will be considered source data, and will not be required to be reported, unless otherwise noted. Demographic data collected at screening will be reported.

The number (%) of participants with maximum postdose QTcF values and maximum increases from baseline in the following categories will be tabulated:

Safety QTcF Assessment

Degree of Prolongation	Mild (ms)	Moderate (ms)	Severe (ms)
Absolute value	>450-480	>480-500	>500
Increase from baseline		30-60	>60

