2.1. Modifications to the Analysis Plan Described in the Protocol

None.

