2.2. Study Objectives, Endpoints, and Estimands

The following are the objectives and endpoints in this study. Estimand framework will not be applied to this Phase 1 study in healthy participants.

Objectives	Endpoints
Primary:	Primary:

 • To determine the relative bioavailability of sisunatovir following a single oral dose of CCI mg as PIC vs WGT in a fasted state 	
 • AUC_{last}, AUC_{inf} (if data permit*), and C_{max} of PIC vs WGT
Secondary:	Secondary:

 • To determine the effect of a high-fat meal on the relative bioavailability of sisunatovir following a single oral dose of CCI mg as WGT • To determine the effect of a low-fat meal on the relative bioavailability of sisunatovir following a single oral dose of CCI mg as WGT • To characterize the safety and tolerability following a single oral dose of CCI mg of sisunatovir as PIC or WGT in a fasted state, or as WGT in a fed state 	
 • AUC_{last}, AUC_{inf} (if data permit*), and C_{max} of WGT under fasted vs with a high-fat meal • AUC_{last}, AUC_{inf} (if data permit*), and C_{max} of WGT under fasted vs with a low-fat meal • Assessment of TEAEs, clinical laboratory abnormalities, vital signs, and 12-lead ECGs
Tertiary/Exploratory:	Tertiary/Exploratory:

 • To determine additional PK parameters of sisunatovir following a single oral dose of CCI mg as PIC or WGT in a fasted state, or as WGT in a fed state 	
 • Additional plasma PK parameters: 
 ○ CL/F and V_z/F as data permit ○ T_{max} ○ $t_{1/2}$, as data permit

*Should it be deemed that too few AUC_{inf} estimates (eg, less than 10 for a single dose) are obtained from the evaluable participants, AUC_{last} may be selected as the primary/secondary endpoint for CSR reporting (otherwise AUC_{last} will be an exploratory endpoint).

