3.2.2. Safety Endpoints

The following data are considered in standard safety summaries (see protocol for collection days, baseline assessment, and list of parameters):

- TEAEs

- laboratory data
- vital signs data
- electrocardiogram (ECG) results

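### The SAP drops the categorical QTcF table that the protocol requires, and declares no change from the protocol

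*SAP*

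**What the plan says.** Protocol 9.3.3.1 states: "The number (%) of participants with maximum postdose QTcF values and maximum increases from baseline in the following categories will be tabulated". The categories are >450-480, >480-500 and >500 ms for the absolute value, and 30-60 and >60 ms for the increase. The same section adds: "Any clinical laboratory, ECG, BP, and pulse rate abnormalities of potential clinical concern will be described".

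Both documents name vital signs and ECGs in a secondary endpoint. In SAP 2.2 it reads "Assessment of TEAEs, clinical laboratory abnormalities, vital signs, and 12-lead ECGs". SAP 3.2.2 introduces its list of TEAEs, laboratory data, vital signs and ECG results with "The following data are considered in standard safety summaries". SAP 3.2.2.3 and 3.2.2.4 then define a baseline and a change from baseline for vital signs and ECGs.

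In the analysis section, SAP 6.2.2.4 says only "ECG data will be databased and available upon request", and SAP 6.2.2.3 says only "Vital sign data will be databased and available upon request". SAP 6.3, on other safety summaries, has the entry None. SAP 2.1, headed "Modifications to the Analysis Plan Described in the Protocol", has the same entry.

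**The concern.** The protocol's commitment to the QTcF table is specific and unqualified. The SAP section that governs ECG data replaces it with storage of the data. Protocol section 9 does permit departures ("The SAP may modify what is outlined in the protocol where appropriate"), but SAP 2.1 says there are none, so a reader would assume the protocol's safety analyses are intact.

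The SAP also disagrees with itself. It places ECGs and vital signs among the data for standard summaries and defines changes from baseline, yet names no output that uses them.

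At stake is the reporting of a named secondary endpoint. Protocol 2.3.1 gives ECG and vital-sign monitoring as the mitigation for the cardiovascular risk, so a reader of the study report would expect to see the result.

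**Working it through.** The discrepancy is textual, and the plan gives no figure to reproduce. The arithmetic below only sizes it.

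**Planned outputs by safety data type (SAP 3.2.2 against SAP 6.2.2)**

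| Data type | Output named in SAP 6.2.2.1 to 6.2.2.4 |
|---|---|
| TEAEs | Reported per the sponsor's data standards (CaPS) |
| Laboratory data | Listed and summarized by treatment per CaPS |
| Vital signs | None; databased |
| ECG | None; databased |

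Two of the four types have a named output. Of the protocol's 3 + 2 = 5 QTcF categories, the SAP mentions none.

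**Scheduled ECGs (Protocol 1.3, Tables 1 and 2).** One ECG is marked on Day 1 of each period and one on the discharge day. The counts are for 12 completers per part and leave out screening, early-termination and unscheduled ECGs.

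- Part 1: 12 × (3 + 1) = 48
- Part 2: 12 × (2 + 1) = 36
- Total: 48 + 36 = 84

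**ECGs after a dose.** SAP 3.2.2.4 takes the last predose Day 1 measurement as baseline, which implies that the single Day 1 ECG is predose. On that assumption:

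- Part 1: Day 1 of Periods 2 and 3, plus discharge: 12 × 3 = 36
- Part 2: Day 1 of Period 2, plus discharge: 12 × 2 = 24
- Total: 36 + 24 = 60

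**Participants with a postdose ECG for each treatment, on the same assumption.** Only the last period of each part contains an ECG after its own dose.

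| Part and treatment | Same period only | Counting the next period's Day 1 ECG |
|---|---|---|
| Part 1, A | 0/12 | 12/12 |
| Part 1, B | 0/12 | 12/12 |
| Part 1, C | 12/12 | 12/12 |
| Part 2, B | 6/12 | 12/12 |
| Part 2, D | 6/12 | 12/12 |

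Without an attribution rule the table would be empty for A and B in Part 1 and half-filled in Part 2.

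**How much the table could show.** Protocol 2.2.4 gives a half-life of 7-10 h and a Tmax of 4-6 h. The fraction of drug left at 72 h is 2^(−72/t½):

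- t½ = 7 h: 2^(−72/7) = 0.0008, about 0.08%
- t½ = 10 h: 2^(−72/10) = 0.0068, about 0.7%

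If 0 of 12 participants fall in a category, the one-sided 95% upper bound on the rate is 1 − 0.05^(1/12) = 0.221, about 22%.

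**The case against.** The best defence is that the general SAP text covers the table. SAP 6.2.2 says safety data will be summarized where appropriate, SAP 3.2.2 lists ECG results among standard summaries, and SAP 5.2.1 presents categorical variables as numbers and percentages. None of these names the QTcF categories, and the ECG-specific section says only that the data are databased. CaPS is not available to us and might include such a table. However, the adverse event and laboratory sections invoke it, and the vital-signs and ECG sections do not.

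A second defence is that the table would say little. This largely stands. The scheduled ECGs come long after Tmax, and with one scheduled postdose ECG per treatment the maximum is simply that value. Protocol 2.2.4 also reports no significant QTc prolongation in earlier concentration-QT analyses. These are reasons for a declared omission; they do not make the entry None correct.

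Three further points are fair:

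- The monitoring that mitigates the risk is done at the site under Protocol 7.1.2, 8.3.3 and Appendix 7, and does not depend on a report table.
- The vital-signs limb is weaker, because the protocol asks only that abnormalities be described and names no table.
- The attribution rule is a new convention for ECGs. It does follow the documents' own practice: Protocol Tables 3 and 4 use the next predose PK sample as the 72-hour sample, and SAP 3.2.2.1 assigns washout events to the previous treatment.

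**Conclusion.** The concern holds. The protocol requires a categorical QTcF table, the SAP does not plan it, and SAP 2.1 denies any change. The protocol allows the SAP to drop the table; the fault is that it does so undeclared.

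This should be corrected, but its reach is limited to safety reporting. Data collection, TEAE reporting, investigator ECG review and the PK endpoints are untouched. The finding is firm for QTcF and softer for vital signs. It rests on the text alone. The count of 60 postdose ECGs, the attribution counts and the 72-hour timing also assume a predose ECG on each Day 1 and full completion of both parts.

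**What to change.** Add to SAP 6.2.2.4, in substance:

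> The number and percentage of participants in each QTcF category of Protocol 9.3.3.1 (maximum postdose value and maximum increase from baseline) will be tabulated by treatment within each part, on the Safety Analysis Set. The predose ECG on Day 1 of Period k+1, about 72 hours or more after the Period k dose, counts as a postdose value for the Period k treatment and also as the Period k+1 baseline.

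In SAP 6.2.2.3, state how blood pressure and pulse rate abnormalities will be described.

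If the QTcF table is dropped on purpose, replace the entry in SAP 2.1 with that change and its reason.

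As an optional clarification, SAP 3.2.2.2 could state the same dual use for laboratory values. The SAP does not forbid it, CaPS may already cover it, and it would not remove a shifted next-period baseline.

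The cost is one SAP paragraph and one table from ECGs already collected, or one entry in SAP 2.1. No new assessments are needed.

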6.3. Other Safety Summaries and Analyses Endpoint(s)

None.

6.4. Exploratory Endpoints

Other plasma PK parameters including CL/F, V_z/F, T_{max} and t_{1/2} will be summarized by treatment group and will include the set of summary statistics as specified in [Table 5](#).

6.5. Subset Analyses

There are no planned subset analyses.

6.6. Baseline and Other Summaries and Analyses

6.6.1. Demographic Summaries

Demographic characteristics will be listed and summarized for Safety Analysis Set in accordance with the CaPS.

6.6.2. Study Conduct and Participant Disposition

Participants evaluation groups will show end of study participant disposition. Frequency counts will be supplied for participant discontinuation(s) by treatment. Data will be reported in accordance with the CaPS.

6.6.3. Study Treatment Exposure

Study treatment exposure will be listed.

6.6.4. Concomitant Medications and Nondrug Treatments

All concomitant medication(s) as well as non-drug treatment(s) will be reported in the listings.

7. INTERIM ANALYSES

No formal interim analysis will be conducted for this study. As this is an open-label study, the sponsor may conduct unblinded reviews of the data during the course of the study for the purpose of safety assessment, facilitating PK modeling, and/or supporting clinical development.

Final analysis will follow the official database release. As this will be an open-label study, there is no formal unblinding of the randomization code.

APPENDICES

Appendix 1. SAS Code for Analyses

An example of the PROC MIXED code is provided below:

For primary objective rBA (Periods 1 and 2):

```
proc mixed data=tab.pk;
  class seq period trt participant;
  model log&var=seq period trt/ ddfm=KR;
  random participant(seq) /subject=participant(seq);
  lsmeans trt;
  estimate 'B vs A' trt -1 1 /cl alpha=0.1;

  ods 'Estimates' out=est&var;
  ods 'lsmeans' out=ls&var;
  ods 'covparms' out=cov&var;
  ods 'tests3' out=tst&var;
run;
```

For secondary objectives high-fat and low-fat FE:

```
proc mixed data=tab.pk;
  class seq trt participant;
  model log&var= seq trt / ddfm=KR;
  random participant(seq) / subject=participant(seq);
  lsmeans trt;
  estimate 'C vs B' trt -1 1 /cl alpha=0.1;

  ods 'Estimates' out=est&var;
  ods 'lsmeans' out=ls&var;
  ods 'covparms' out=cov&var;
  ods 'tests3' out=tst&var;
run;

proc mixed data=tab.pk;
  class seq trt participant;
  model log&var= seq trt / ddfm=KR;
  random participant(seq) / subject=participant(seq);
  lsmeans trt;
  estimate 'D vs B' trt -1 1 /cl alpha=0.1;

  ods 'Estimates' out=est&var;
  ods 'lsmeans' out=ls&var;
  ods 'covparms' out=cov&var;
  ods 'tests3' out=tst&var;
run;
```

/* Letter assignments for treatments (trt) within the estimate statement above are as follows

A: Single dose of sisunatovir [REDACTED] mg as PIC under fasted condition;
 B: Single dose of sisunatovir [REDACTED] mg as WGT under fasted condition;
 C: Single dose of sisunatovir [REDACTED] mg as WGT with a high-fat meal.
 D: Single dose of sisunatovir [REDACTED] mg as WGT with a low-fat meal. */

Appendix 2. List of Abbreviations

Abbreviation	Term
%CV	coefficient of variation
AE	adverse event
AUC _{extrap%}	the percent of AUC _{inf} based on extrapolation
AUC _{inf}	area under the concentration-time curve from time 0 to infinity
AUC _{last}	area under the concentration-time curve from 0 to time of last measurable concentration
BLQ	below the limit of quantification
BP	blood pressure
CaPS	Clinical Data Interchange Standards Consortium and Pfizer Standards
CI	confidence interval
C _{last}	estimated plasma concentration at the last quantifiable time point estimated from the log-linear regression analysis
CL/F	apparent clearance
C _{max}	maximum observed plasma concentration
CRU	clinical research unit
CSR	clinical study report
ECG	electrocardiogram
HR	heart rate
k _{el}	the terminal phase rate constant calculated by a linear regression of the loglinear concentration-time curve
LLQ	lower limit of quantification
mg	milligram
ms	millisecond
N/A	not applicable
NC	not calculated
ND	not done
NS	no sample
PIC	Powder in Capsule
PK	pharmacokinetic(s)
PR	time from the beginning of the P wave to the beginning of the QRS complex
QRS	Combination of Q-, R- and S- wave on an electrocardiogram representing ventricular depolarization
QT	time from the start of the Q- wave to the end of T- wave, which represents time taken for ventricular depolarization and repolarization
QTc	corrected QT
QTcF	corrected QT (Fridericia method)
r ²	goodness of fit statistic from the log-linear regression
rBA	relative bioavailability
RR	respiratory rate
RSV	respiratory syncytial virus

Abbreviation	Term
SAP	statistical analysis plan
SD	standard deviation
SoA	schedule of activities
$t_{1/2}$	terminal elimination half-life
TEAE	treatment emergent adverse event
T_{max}	time to reach C_{max}
V_z/F	apparent volume of distribution for extravascular dosing
WGT	Wet Granulation Tablet
